Many adolescents with T1D struggle with a vicious cycle in which the insulin resistances of obesity and puberty necessitate ever higher doses of insulin, which contribute to additional weight gain that further exaggerates insulin resistance. This is illustrated by the large proportion of adolescents and young adults in the T1D Exchange (T1DX) Registry who are unable to achieve and maintain HbA1c levels in the target range (3). When compared to participants with well controlled diabetes in the T1DX Registry, adolescents and young adults with poorly controlled T1D were nearly two-fold more likely to have BMI >85% (4), however, the characteristics of this obesity/puberty phenotype are unknown. For example, obesity in adolescents with T1D may lead to severe hepatic, as well as peripheral insulin resistance, which contributes to post-meal hyperglycemia and increased HbA1c levels due to inability of pre-meal boluses to suppress endogenous glucose production.

The rate of overweight and obesity in patients with T1D mirror that seen in the general population nationwide (5), with recent data from the T1DX revealing that 40% or more adolescents and young adults are overweight or obese (3). Our experience in the Yale Pediatric Diabetes Program reflects similar rates of this new phenotype, and we may expect further increases in the prevalence of obesity in T1D as clinicians attempt to optimize metabolic control with insulin alone. The much anticipated availability of the first commercial hybrid closed loop (HCL) insulin delivery system has been shown to significantly improve diabetes management in a multitude of ways: lower HbA1c, increased time in target sensor glucose range, less frequent hypoglycemia (6), and decreased diabetes burden (7). However, the improved glycemic control seen in adolescents was accompanied by an 8% increase in total daily insulin dose, as well as 1 kg weight gain during three months of study. While the increase in weight in adolescents in this study did not reach statistical significance, the findings in the much larger group of adults of a 1.4 kg weight increase in three months was statistically significant (6). Increases in weight are not surprising, as increases in daily insulin doses are associated with weight gain (8), which is mediated in part by reductions in renal glucose excretion.

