I anticipate that the results of this proposal will help to inform future studies of SGLT2 inhibitors in pediatric patients with T1D. Moreover, identification of markers associated with insulin resistance and progression of fatty liver disease ⁶ will facilitate identification of participants who stand to benefit from treatment in future studies.

Future projects to understand and the scientific premise, rationale, and mechanisms of adjunctive therapies in T1D

In broad terms, treatment of T1D has not changed in almost 100 years; simply more and better types of insulin delivered in different ways. Thus far, the only adjunctive agent studied in youth with T1D is metformin, but the benefits of treatment with this agent were disappointing. Yale was one of the centers

in the recent randomized clinical trial of metformin carried out by the T1D Exchange (T1DX) Study Group in overweight and obese adolescents with T1D. That study showed that adjunctive treatment with metformin did not result in improved glycemic control, although there were small reductions in insulin dose and BMI z-scores (32). The T1DX metformin study was the first and only study to date aimed at treating this new phenotype of youth with obesity and T1D. Furthermore, our group has found only modest improvements in postprandial glycemic excursions with use of a GLP-1 agonist in adults with T1D (33).

There are a number of reasons why SGLT2 inhibitors are particularly attractive agents for adjunctive treatment of overweight and obese individuals with T1D: several drugs in this class have been approved for use in adults with T2D; their mechanism of action does not depend on stimulation of endogenous insulin secretion; treatment with these agents lowers weight, blood pressure, and HbA1c; and recent studies indicate that these agents have cardio- and reno-protective benefits (34).

Sophisticated metabolic studies in adults with T2D have shown improvements in insulin sensitivity (35,36), likely due to decreasing glucotoxicity; results that should be translatable to T1D. In fact, improved HbA1c, fasting glucose, increased time in range, as well as decreased insulin requirements and weight loss, have been seen when SGLT2i are used as adjunctive therapies in adults with T1D (37-39). Moreover, use of an oral medication may be less burdensome than additional injectables for future use in youth with T1D who already struggle with current diabetes management tasks.

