Investigators have demonstrated that two to four weeks of treatment with SGLT2i results in a shift from glucose oxidation to fat oxidation (35,36) in adults with T2D. Additionally, a small study has shown that SGLT2i therapy lowers ALT in adults with T2D and ultrasound diagnosed hepatic steatosis, unrelated to weight loss (40).

4. **Research Plan:** Summarize the study design and research procedures using non-technical language that can be readily understood by someone outside the discipline. Be sure to distinguish between standard of care vs. research procedures when applicable, and include any flowcharts of visits specifying their individual times and lengths. Describe the setting in which the research will take place.

Overview: This is a cross-sectional study of 72 adolescents and 36 young adults with T1D who will undergo comprehensive metabolic evaluation. The study consists of 2 visits which will take place over approximately 30 days. The study aims to enroll 36 adolescents with T1D and overweight/obesity, 36 lean adolescents with T1D, and 36 young adults with T1D. To characterize the impact of adiposity on metabolism during puberty, adolescents will undergo the euglycemic hyperinsulinemic clamp study with tracer enhancement and DEXA scan on the Hospital Research Unit, and abdominal MRI in the Magnetic Resonance Resource Center. The lean young adults with T1D will provide a control group to reflect prepubertal youth with T1D, and will undergo the euglycemic hyperinsulinemic clamp study with tracer enhancement and DEXA scan.

Subjects: This study will enroll 36 obese/overweight and 36 lean adolescents (Tanner stage 2-5) with T1D. A comparison control group of 36 lean young adults with T1D will also be enrolled, since they will be unaffected by the adverse metabolic effects of puberty or obesity.

Study visits: Enrollment and both study visits will take place over approximately 30 days. All participants will undergo screening to evaluate study eligibility through the elicitation of a medical history and physical examination and laboratory tests.

Enrollment: Screening will be conducted by invitation to potentially eligible subjects during which written informed consent will be obtained prior to conducting any study related procedures. After informed consent has been obtained and documented, subjects will undergo a history and directed physical exam, anthropometric measures, and hemoglobin A1c. A HbA1c done in the past 30 days may be used.

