- i. the types of future research to be conducted using the materials, specifying if immortalization of cell lines, whole exome or genome sequencing, genome wide association studies, or animal studies are planned *Write here*
- ii. the plan for the collection of material or the conditions under which material will be received *Write here*
- iii. the types of information about the donor/individual contributors that will be entered into a database *Write here*
- iv. the methods to uphold confidentiality *Write here*

B. What are the conditions or procedures for sharing of materials and/or distributing for future research projects? *Write here*

C. Is widespread sharing of materials planned? *Write here*

D. When and under what conditions will materials be stripped of all identifiers? *Write here*

E. Can donor-subjects withdraw their materials at any time, and/or withdraw the identifiers that connect them to their materials? *Write here*

- i. How will requests to withdraw materials be handled (e.g., material no longer identified: that is, anonymized) or material destroyed? *Write here*

F. Describe the provisions for protection of participant privacy *Write here*

G. Describe the methods for the security of storage and sharing of materials *Write here*

6. **Subject Population:** Provide a detailed description of the types of human subjects who will be recruited into this study.

This study aims to enroll 36 obese/overweight adolescents and 36 lean adolescents with T1D. A comparison control group of 36 lean young adults with T1D matched for gender and HbA1c will also be enrolled, since they will be unaffected by the adverse metabolic effects of puberty or obesity.

7. **Subject classification:** Check off all classifications of subjects that will be specifically recruited for enrollment in the research project. Will subjects who may require additional safeguards or other considerations be enrolled in the study? If so, identify the population of subjects requiring special safeguards and provide a justification for their involvement.

 Children	 Healthy	 Fetal material, placenta, or dead fetus
 Non-English Speaking	 Prisoners	 Economically disadvantaged persons
 Decisionally Impaired	 Employees	 Pregnant women and/or fetuses

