Associations of these assessments with measures of insulin sensitivity will be explored for all groups. Unadjusted differences in the group means of primary and secondary outcomes of interest between lean and obese adolescent subjects, as well as between lean young adults and lean adolescent subjects, will be examined using the Student's t-test or the Mann-Whitney U test for variables with Gaussian and not normal distributions respectively. The impact of group, gender, sex hormones, pubertal stage, and growth factors on the outcome measures will also be explored using multivariable linear regression modeling. For the primary adjusted analysis, we will treat group as a categorical variable, and conduct two post-hoc pair-wise comparisons of means at alpha of 0.025. For the secondary adjusted analysis, we will also treat our three groups of subjects as an ordinal variable, whereby the lowest level will be given to the obese adolescents, followed by the lean adolescents, and then lean young adults. The latter approach will allow us to obtain a linear increase in the mean glucose disposal rate across the three groups, thus allowing us to use an alpha level of 0.05. The outcome variable will be normalized, if needed, using the natural log function.

Visit 2: Abdominal MRI: Sample Size: Based on mean hepatic lipid content in healthy overweight/obese and lean children ¹⁰, groups sizes of 36 lean and 36 obese adolescents will achieve >99% power at alpha of 0.05 to detect a difference between group means of 3.5% (SD=2) and 1.5% (SD=0.5). Even if a few subjects decline participation in this Aim, we will still have 90% power at alpha of 0.05 to detect the projected effect size using with a minimum of 12 subjects per group.

Data Analysis Approach:

The Proton Density Fat Fraction (PDFF) , a biomarker for hepatic steatosis, will be calculated from the liver images obtained liver PDFF parametric maps ⁹. A PDFF value above 5.5% is indicative of fatty liver ¹¹.

• Statistical Analysis: Descriptive statistics (mean, standard deviation, count, and percent) will be used to characterize the groups. Continuous variables will be compared between the lean and obese adolescents using either the Student's t-test or the Mann-Whitney U test. Categorical variables will be compared with the Chi-square test or the Fisher's Exact test. Associations of the following assessments with hepatic fat fraction will be explored through Spearman Correlation.

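### Young adults are matched on HbA1c but the adjusted model omits it, and beyond the 9% limit nothing balances HbA1c between lean and obese adolescents

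*Combined protocol and SAP*

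**What the plan says.** Section I, item 6 (Subject Population) attaches matching to one group only: "lean young adults with T1D matched for gender and HbA1c will also be enrolled". It does not say which adolescent group is the reference, whether matching is individual or by frequency, or how close it must be. For the adolescents it gives numbers and no balancing rule: "This study aims to enroll 36 obese/overweight adolescents and 36 lean adolescents with T1D". The eligibility criteria (item 8) apply the same upper HbA1c limit of 9% to all three groups.

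HbA1c is obtained at enrolment (item 4), where "A HbA1c done in the past 30 days may be used", so it is available as a covariate.

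In item 13 the adjusted analysis is described thus: "The impact of group, gender, sex hormones, pubertal stage, and growth factors on the outcome measures will also be explored using multivariable linear regression modeling". HbA1c is not in the list. The two pairwise contrasts from this model are each tested at 0.025, and the unadjusted versions use independent-sample tests. By name, HbA1c enters the Visit 1 analysis only as an exploratory Spearman correlate of hepatic and peripheral insulin action.

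**The concern.** The design treats HbA1c as important enough to match on, but the model does not carry it. The two contrasts are affected differently.

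**Lean young adults versus lean adolescents.** Matching removes the HbA1c part of the variability between the group means. A model without HbA1c still counts that part in its residual variance, so the reported standard error is larger than the true one and the test is conservative.

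**Lean versus obese adolescents.** The groups are formed by BMI, and no matching or randomisation balances HbA1c. The background (item 3) reports that in a registry "adolescents and young adults with poorly controlled T1D were nearly two-fold more likely to have BMI >85" percent. It also attributes improved insulin sensitivity under another therapy to a fall in glucose toxicity ("likely due to decreasing glucotoxicity"). If both links hold here, part of a lean-obese difference could reflect glycaemic control, and the plan has no prespecified analysis to show how much.

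**Working it through.** **Inputs from item 13:** 36 per group; SD 3; means 13.6 and 11.5, so a difference of 2.1 mg/kg lean mass/min; alpha 0.025, taken as two-sided because the plan does not say.

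**Assumptions, since the documents give no values:** HbA1c explains 5-15% of outcome variance (R²); lean and obese adolescents differ by 0.5 HbA1c points; the outcome falls by 0.5-1.0 per point; HbA1c SD is 0.8-1.0 points.

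**1. The plan's own figure.** The standard error of a difference is 3 × √(2/36) = 0.707, and 2.1/0.707 = 2.97. With a critical t of 2.291 on 70 df, power is 75.0% (76.7% by the normal approximation). A one-sided test at 0.025 gives 83.4%. Neither is the stated 80%. That is a separate matter, and 75.0% serves here only as the baseline for step 4.

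**2. Young-adult contrast.** Suppose matching makes mean HbA1c equal in the two groups. The true SD of the difference is then the reported standard error times √(1 − R²). The test rejects beyond 2.241 reported standard errors, which is 2.241/√(1 − R²) true ones.

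| R² | Reported SE too large by | Effective cut-off | Actual two-sided error |
|---|---|---|---|
| 0.05 | 2.6% | 2.300 | 2.1% |
| 0.10 | 5.4% | 2.363 | 1.8% |
| 0.15 | 8.5% | 2.431 | 1.5% |

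In this approximation the result depends on R² and not on the SD or group size.

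**3. Lean-obese contrast.** The share carried by HbA1c is difference × slope: 0.5 × 0.5 = 0.25 and 0.5 × 1.0 = 0.5. As shares of 2.1 these are 12% and 24%. In standard errors they are 0.25/0.707 = 0.354 and 0.5/0.707 = 0.707. With no other group effect, the noncentral t on 70 df puts the error rate at 3.4% and 6.3% instead of 2.5%.

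A wider grid uses r × d × 3, where r is the within-group HbA1c-outcome correlation (0.1-0.5) and d the HbA1c difference in SD units (0.25-1.0). It gives 0.075 to 1.5, or 4% to 71% of 2.1. The top of that range needs both extremes at once.

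**4. Does adjustment raise lean-obese power?** The effective SD after adjustment is 3 × √(1 − r²) × √(1 + d²/4), with r = slope × HbA1c SD/3 and d = 0.5/HbA1c SD. Power is for the same 2.1 difference, 69 df:

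| HbA1c SD | Slope | r | d | Effective SD | Power |
|---|---|---|---|---|---|
| 0.8 | 0.5 | 0.133 | 0.625 | 3.115 | 71% |
| 0.8 | 1.0 | 0.267 | 0.625 | 3.029 | 74% |
| 1.0 | 0.5 | 0.167 | 0.500 | 3.049 | 73% |
| 1.0 | 1.0 | 0.333 | 0.500 | 2.915 | 78% |

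Against 75.0% unadjusted there is no dependable gain. If the glycaemic share is also taken out of the target, leaving 2.1 − 0.25 = 1.85 or 2.1 − 0.5 = 1.6, power is about 48-61%. A rise to 77%, 80% and 82% at R² of 5%, 10% and 15% occurs only if the two groups have equal HbA1c, the opposite of the case in step 3.

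**The case against.** The strongest objection is causal. The background says that obesity may produce hepatic and peripheral insulin resistance, which in turn raises HbA1c. On that path HbA1c follows from the outcome, and adjusting the lean-obese contrast for it would remove part of the effect under study. This stands. Omitting HbA1c from the main lean-obese model is defensible, and a reader who infers that HbA1c is simply a confounder there goes further than the documents.

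The supporting links are also modest. The glucose-toxicity remark concerns adults with type 2 diabetes, and the plan says only that the result should carry over. The registry comparison was not limited to an HbA1c of 9% or below, as far as the plan reports it, whereas this study is. The limit bounds an imbalance without removing it.

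The plan would show some of the problem already. Descriptive statistics and three-group comparisons of continuous variables would display an HbA1c difference, and the Spearman correlations would show its link to insulin action. Neither adjusts a group contrast.

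Finally, a reader might infer that the matching is ignored altogether, or that unpaired tests are wrong. Gender, the other matching factor, is in the regression. If the matching is by frequency, unpaired tests are acceptable, and omitting a balanced factor costs precision without biasing the young-adult contrast.

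**Conclusion.** The point holds for HbA1c specifically, and differently for each contrast. For young adults versus lean adolescents, the omission makes the test conservative, at about 1.5-2.1% instead of 2.5%. This assumes that HbA1c explains 5-15% of outcome variance and that matching is close and made to the lean adolescents. For lean versus obese adolescents, a glycaemic share of 12-24% of the planned difference is possible under the stated assumptions, and no prespecified analysis would reveal it. That is a gap in sensitivity analysis, not an error in the main model.

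Two further inferences are not supported. Step 4 shows that adjustment cannot be relied on to raise lean-obese power. A case for adjusting for diabetes duration has no basis either: the documents require at least 12 months, give no durations by group, and do not link duration to insulin sensitivity.

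**What to change.** In item 13, fit the primary adjusted model with and without enrolment HbA1c and state in advance which contrast is read from which.

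- **Lean young adults versus lean adolescents:** use the model that includes HbA1c beside gender. Matching has already held HbA1c level by design, so this corrects the standard error without changing the question asked.
- **Lean versus obese adolescents:** keep the model without HbA1c as the main analysis. Prespecify the HbA1c-adjusted contrast as a sensitivity analysis, read as the difference not carried by glycaemic control, and say why it is not the main estimate.
- **Item 6:** state which adolescent group the young adults are matched to, the type of matching and the tolerance.

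The cost is a few sentences and one extra model, with no new measurements. The downside is that the adjusted lean-obese estimate may be conservative, which is why it should stand beside the main one and not replace it.

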- i. How will adverse events and unanticipated problems involving risks to subjects or others be reported, reviewed and managed? *Write here*
- ii. What provisions are in place for management of interim results? *Write here*
- iii. What will the multi-site process be for protocol modifications? *Write here*

13. **Statistical Considerations:** Describe the statistical analyses that support the study design.

Visit 1 Euglycemic Hyperinsulinemic Clamp: Sample Size: Prior work evaluating insulin sensitivity in youth with T1D is limited in consistency in reporting insulin-mediated glucose disposal. Thus, for sample size calculation, glucose infusion rate will be utilized as this calculation is more consistent across studies and can provide a good estimate of glucose disposal. A clinically meaningful difference would be at least 20% reduction in mean glucose disposal rate from lean to obese. In addition, we expect T1D lean young adults to have the highest mean glucose infusion rate, reflecting the anticipated response in T1D children not affected by hormonal changes of puberty (2). Therefore, we propose to compare the three means in a sequential manner: obese vs. lean adolescents with T1D, and lean adolescents with T1D vs. lean young adults with T1D, thus reducing the alpha level of 0.05 by $\frac{1}{2}$.

Using published literature (43,44), we will need 36 lean and 36 obese/overweight pubertal adolescents with T1D, to have 80% at alpha of 0.025, to detect a difference between group means of 13.6 (SD=3) and 11.5 mg/kg lean body mass/min (SD=3); and 36 lean young adults to detect a minimum percent increase in glucose infusion rate in the range of 15-18% from that of lean pubertal adolescents with T1D - for the respective sequential group comparisons. Of note, the literature suggests that the actual increase for the latter is around 30% ², therefore, we should be sufficiently powered.

An interim analysis will be conducted when we recruit 15 subjects in each group. If significant differences will be observed at that time, we will reconsider the sample size.

Data Analysis Approach: The departmental biostatistician [name], will guide [name] in analysis.

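### The stated 80% power for lean versus obese adolescents is 75% if alpha 0.025 is two-sided, and the protocol does not state sidedness

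*Combined protocol and SAP*

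**What the plan says.** The Visit 1 Sample Size paragraph (Section I, item 13) plans two comparisons of glucose infusion rate: obese versus lean adolescents, and lean adolescents versus lean young adults. It explains the significance level as "thus reducing the alpha level of 0.05 by" one half. It then states the requirement: "we will need 36 lean and 36 obese/overweight pubertal adolescents with T1D, to have 80% at alpha of 0.025". The word power is missing but clearly meant. The inputs are means of 13.6 and 11.5 mg/kg lean body mass/min, with SD 3 in each group. For the second comparison, 36 young adults are said to allow detection of an increase of 15-18%. The same paragraph sets the relevance threshold: "A clinically meaningful difference would be at least 20% reduction in mean glucose disposal rate from lean to obese".

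The Visit 1 Statistical Analysis text says unadjusted differences "will be examined using the Student's t-test or the Mann-Whitney U test". For the primary adjusted analysis it will "conduct two post-hoc pair-wise comparisons of means at alpha of 0.025". The Visit 2 Sample Size paragraph claims "90% power at alpha of 0.05 to detect the projected effect size using with a minimum of 12 subjects per group", for means of 3.5% (SD 2) and 1.5% (SD 0.5). None of these places says whether the tests are one-sided or two-sided.

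**The concern.** Every input to the power statement is printed, so it can be checked directly. At two-sided 0.025, 36 per group falls short of 80%. At one-sided 0.025 it exceeds 80%. The missing word therefore decides whether the justification holds.

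Obese versus lean adolescents is the comparison in the study title and the first stated purpose. If power is 75%, the chance of missing a true difference of the size used for planning is 25%, not 20%. No allowance for loss is stated for Visit 1, and 36 per group is also the enrolment target, so nothing is in reserve.

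The halving of alpha is not in question. It is a valid split for two comparisons that are not gated on each other.

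**Working it through.** **Inputs** (Section I, item 13, Visit 1 Sample Size): n = 36 per group; difference 13.6 − 11.5 = 2.1, which is 2.1/13.6 = 15.4%; SD 3; alpha 0.025. Standardised difference d = 2.1/3 = 0.70. Test: Student's t-test, as named in the analysis text.

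**Formula.** Degrees of freedom 2n − 2 = 70. Noncentrality = d × √(n/2) = 0.70 × √18 = 2.970. Power is the probability that a noncentral t variable with these parameters exceeds the critical value (either tail for a two-sided test).

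**Attempt to reproduce the stated 80% with 36 per group**

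| Reading of 0.025 | Critical t | Power, t-test | Power, normal approximation | n per group for 80% (t-test) |
|---|---|---|---|---|
| Two-sided | 2.291 | 75.0% | 76.7% | 41 (40 gives 79.9%) |
| One-sided | 1.994 | 83.4% | 84.4% | 34 |

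A simulation of 200,000 trials gave 75.1% two-sided and 83.5% one-sided. If the Mann-Whitney test is used on normal data, two-sided power is about 72-73%. Unadjusted two-sided 0.05 also gives 83.4%, but that contradicts the 0.025 in both the sample size and the analysis text.

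**Which reading the protocol supports**

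1. The 0.025 is obtained by dividing 0.05 between two comparisons, not between two tails. Reading it as one-sided would make the starting 0.05 one-sided, which is stated nowhere.
2. Visit 2: difference 2.0, pooled SD √((2² + 0.5²)/2) = √2.125 = 1.458, n = 12, alpha 0.05. Noncentrality = (2.0/1.458) × √6 = 3.361 on 22 degrees of freedom. Two-sided power is 89.4%, close to the stated 90%. One-sided power is 94.6%.
3. Young adults: with SD 3 assumed, the smallest difference detectable with 80% power at two-sided 0.025 is 0.740 × 3 = 2.22, and 2.22/13.6 = 16.3%, inside the stated 15-18%. The one-sided value is 2.01/13.6 = 14.8%, just below that range.

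**Sensitivity (two-sided 0.025)**

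- A 20% reduction is 0.20 × 13.6 = 2.72. Noncentrality = (2.72/3) × √18 = 3.847; power 93.8%.
- With the difference held at 2.1, an SD of about 2.84 would give 80% with 36 per group.
- With 32 evaluable per group (an assumed loss), power is 69%.

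**Holm across the two comparisons** (simulation, 400,000 runs, shared lean group, SD 3 in all groups). The smaller p-value is tested at 0.025 and, if significant, the other at 0.05.

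| True young-adult increase | Power, obese vs lean |
|---|---|
| 0% | 75.1% |
| 15% | 82.1% |
| 18% | 82.9% |
| 30% | 83.4% |

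With no true differences, the family-wise error is 4.6% under Holm or the flat 0.025. It would be 9.1% if both comparisons were simply tested at 0.05.

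**The case against.** **Sidedness is inferred.** The Visit 2 check assumes a pooled t-test, while the plan also allows Mann-Whitney. A one-sided Mann-Whitney convention comes near both figures: about 90% for Visit 2 with 12 per group, and about 81-82% for Visit 1 with 36. The protocol also expects a direction, with young adults highest. The Visit 2 match is therefore supporting evidence, not proof. But no text adopts one-sided tests or sizes the study on Mann-Whitney, and the multiplicity origin of 0.025 and the 15-18% range still point to two-sided.

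**The primary adjusted analysis is a regression.** The 75% is the power of an unadjusted comparison. If covariates were unrelated to group and explained 10% of the variance, power would be about 80%; at 15%, about 82%. This stands as a qualification. The documents give no such figure, pubertal stage and sex hormones may be related to group and so reduce precision, and the sample size text uses unadjusted means and SDs.

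**Rounding.** An SD of 2.84 prints as 3, so unrounded source values could close the gap. They could equally widen it. The printed inputs do not support the printed power.

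**Small impact, and Holm is a choice.** Both are fair. Power is 94% at the protocol's own 20% threshold, and Holm changes the testing procedure, so it is an option and not part of the arithmetic correction.

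**Conclusion.** The concern holds. Sidedness is not stated, and on the better-supported two-sided reading the planned 36 per group gives 75.0% power for the 2.1 difference, 5 points below the stated 80%. Reaching 80% would take 41 per group. The 80% is met only if 0.025 is one-sided (83.4%).

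These figures assume an unadjusted t-test, normal data, SD 3 exactly, and all 36 per group evaluable. The shortfall does not threaten the study at the 20% reduction it calls clinically meaningful, where power is 94%. It should be corrected because it misstates the justification for the main comparison.

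**What to change.** In the Visit 1 Sample Size and Statistical Analysis text, state that the pairwise tests are two-sided. Restate power with 36 per group as 75% for a difference of 2.1 (15.4%) and 94% for a 20% reduction. Give a minimum detectable young-adult increase of about 16%, assuming SD 3. This is wording only; the cost is a less favourable power figure.

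Alternatively, replace the flat 0.025 in both places with Holm across the two comparisons. This keeps the family-wise error of the two final tests at or below 0.05, with no gate and no extra subjects. It is a change to the testing procedure, and it brings no real gain for obese versus lean if young adults do not differ from lean adolescents. It also does not cover the interim analysis at 15 per group, which needs its own rule.

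Keeping both the flat two-sided 0.025 and 80% power would require 41 lean and 41 obese/overweight adolescents: 2 × (41 − 36) = 10 more than planned.
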